### **3.0 Introduction**

This statistical analysis plan (SAP) describes the statistical analysis to be completed by AbbVie Statistics and Statistical Programming for study Protocol M13-101 dated 26 June 2015 and incorporates 10 amendments and 5 administrative changes. The SAP provides details to further elaborate statistical methods as outlined in the protocol and describes analysis conventions to guide the statistical programming work.

This is the first version of the SAP for Protocol M13-101. Unless noted otherwise, all analyses will be performed using SAS version 9.3 or later (SAS Institute Inc., Cary, NC 27513) under the UNIX operating system.

### **4.0 Study Objectives, Design and Procedures**

#### **4.1 Objectives**

##### **4.1.1 Primary Objective**

The primary objective of this study is to evaluate the safety and antiviral efficacy, defined as the percentage of subjects with sustained virologic response 12 weeks post-dosing (SVR12; HCV RNA < LLOQ 12 weeks after the last dose of study drug), of the study regimen.

##### **4.1.2 Secondary Objective**

The secondary objectives of this study are:

- to evaluate the percentage of subjects with sustained virologic response 24 weeks post-dosing (SVR24; HCV RNA < LLOQ 24 weeks after the last dose of study drug) and
- to evaluate the percentage of subjects with extended rapid virologic response (eRVR) (HCV RNA < LLOQ at Weeks 4 through 12 of therapy with ABT-450/r plus ABT-267 plus pegIFN plus RBV).

[figure not shown]
## 4.2 Design Diagram

This is a multicenter, Phase 2, open-label, single-arm, combination treatment study evaluating ABT-450/r in combination with ABT-267, pegIFN and RBV for 24 weeks followed by pegIFN and RBV alone for an additional 24 weeks in HCV genotype 1-infected subjects who have experienced virologic failure while participating in a previous pegIFN-free Abbott/AbbVie DAA combination study. This study consists of a pre-screening period, a screening period and three substudies:

- Substudy 1 (Treatment Intensification [TI]): 24 weeks of therapy with ABT-450/r plus ABT-267 plus pegIFN plus RBV;
- Substudy 2 (pegIFN/RBV [PR] Treatment): 24 weeks of pegIFN and RBV therapy alone;
- Substudy 3 (Post-treatment [PT] Follow-up Period): 48 weeks after last dose of any study drug for resistance monitoring and HCV RNA viral load testing.

A study schematic is shown below (Figure 1).

**Figure 1. Study M13-101 Schematic**

There is one treatment group for this study. During Substudy 1 (TI Period), subjects will receive ABT-450/r 200/100 mg daily (QD), ABT-267 25 mg QD, pegIFN 180 µg once weekly, and weight-based RBV twice daily. During Substudy 2 (PR Treatment

Period), subjects will receive 24 weeks of pegIFN/RBV. All subjects who receive at least one dose study drug will be followed for 48 weeks in the Post-Treatment period. The duration of the study will be 96 weeks, not including a screening period.

### **4.3 Sample Size**

There is no predetermined sample size for this study. Subjects who experience virologic failure in previous Abbott/AbbVie DAA combination studies and who meet the eligibility criteria will be treated in this study.

### **4.4 Interim Analysis**

There will be no interim analysis. Final analysis will occur after all enrolled subjects have completed the Post-Treatment Period or prematurely discontinued from the study. Data will be locked after performing appropriate data cleaning.

## **5.0 Analysis Populations**

### **5.1 Definition for Analysis Populations**

#### **Intent-to-Treat (ITT) Population**

The intent-to-treat (ITT) population will consist of all enrolled subjects who receive at least one dose of study drug. Efficacy analyses will be performed on the ITT population.

#### **Modified Intent-to-Treat (mITT) Population**

A sensitivity analysis of SVR12 as described in Section 10.4, when applicable, will be performed on the intent-to-treat population modified to exclude subjects who are not of HCV genotype 1 infection and the subjects who did not achieve SVR12 for reasons other than virologic failure (mITT-GT-VF).

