5.4.1.1 Virologic Failure Criteria

During the Treatment Period and Follow-up Period of the study, the virologic data will be reviewed by the investigator to evaluate if subjects have met virologic failure criteria.

The following criteria will be considered evidence of virologic failure:

- Failure to achieve HCV RNA level $< 1,000$ IU/mL at TI Week 4. Subject will stop all DAAs and continue pegIFN and RBV at the investigator's discretion.
- Failure to achieve at least a $2 \log_{10}$ IU/mL HCV RNA reduction from baseline at TI Week 12. Subject will stop all study drugs.
- HCV RNA ≥ 25 IU/mL at TI Week 24. Subject will stop all study drugs.
- Confirmed HCV RNA increase of $> 1 \log_{10}$ from nadir (defined as 2 consecutive HCV RNA measurements $> 1 \log_{10}$ IU/mL above nadir) in HCV RNA at any time-point. Subject will stop all study drugs.
- Confirmed breakthrough or relapse: HCV RNA \geq LLOQ (defined as 2 consecutive HCV RNA measurements \geq LLOQ) at any point after HCV RNA $<$ LLOQ. Subject will stop all study drugs (if applicable).

For the latter 2 criteria, confirmatory testing should be completed as soon as possible. If the investigator feels that a subject who meets one of these criteria should still remain on DAA + pegIFN + RBV or pegIFN + RBV treatment, the subject would only be allowed to remain on DAA + pegIFN + RBV or pegIFN + RBV treatment with approval of the AbbVie Study Designated Physician.

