### **Definitions for Efficacy Endpoints**

Note that a confirmed quantifiable post-treatment value is defined as any two consecutive post-treatment HCV RNA measurements  $\geq$  LLOQ. During treatment, a confirmed quantifiable value is defined as any two consecutive HCV RNA values  $\geq$  LLOQ, either both during treatment or at the final treatment measurement and the next consecutive post-treatment measurement.

**RVR** (Rapid Virologic Response) = HCV RNA < LLOQ at TI Week 4.

**eRVR** (extended rapid virologic response) = HCV RNA < LLOQ at TI Weeks 4 through 12 without a confirmed HCV RNA  $\geq$  LLOQ between TI Weeks 4 and 12.

**Final Treatment Visit Response** = HCV RNA < LLOQ at the end of treatment (i.e., at completion of all study drugs: DAAs, pegIFN, and RBV); this corresponds to the Final Treatment Visit value (see Section 6.0).

**Breakthrough** = confirmed increase from nadir in HCV RNA (two consecutive HCV RNA measurements  $> 1 \log_{10}$  IU/mL above nadir) at any time point during treatment or confirmed HCV RNA  $\geq$  LLOQ after HCV RNA  $<$  LLOQ during treatment. A single breakthrough value ( $\geq$  LLOQ or  $> 1 \log_{10}$  above nadir) followed by lost to follow-up would be considered a breakthrough (i.e., will not require confirmation).

**On-treatment virologic failure = breakthrough** or failure to suppress during treatment (all on-treatment values of HCV RNA  $\geq$  LLOQ ) with at least 6 weeks (defined as active study drug duration  $\geq 36$  days) of treatment.

**SVR24** (referred to as SVR24actual in the protocol) = HCV RNA  $<$  LLOQ in the SVR24 window (24 weeks after the last actual dose of study drug [including DAA, pegIFN, and RBV]) without any confirmed quantifiable ( $\geq$  LLOQ) post-treatment value before or during that SVR window.

**SVR12** (referred to as SVR12actual in the protocol) = HCV RNA  $<$  LLOQ in the SVR12 window (12 weeks after the last actual dose of study drug [including DAA, pegIFN, and RBV]) without any confirmed quantifiable ( $\geq$  LLOQ) post-treatment value before or during that SVR window.

**SVR4** = HCV RNA  $<$  LLOQ in the SVR4 window (4 weeks after the last actual dose of active study drug) without any confirmed quantifiable ( $\geq$  LLOQ) post-treatment value before or during that SVR window.

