#### **Reasons for SVR12 Non-response**

Subjects who do not achieve SVR (SVR12 non-responders) will be categorized as having:

1. On-treatment virologic failure (see **On-treatment virologic failure** definition);
2. Relapse (defined according to the **Relapse12** definition for subjects who complete treatment);
3. Prematurely discontinued study drug with no on-treatment virologic failure (defined as any SVR12 non-responder who prematurely discontinued study drug and did not meet the **On-treatment virologic failure** definition);
4. Missing follow-up data in the SVR12 window defined as any subject who completed study drug without data in the SVR12 window after applying the imputation rules and not meeting the definitions of (1), (2), or (3)];
5. Other (defined as any SVR12 non-responder not meeting the definitions of (1) – (4), such as a subject with a single quantifiable value within the SVR12 window followed by an undetectable value beyond the SVR12 window).

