#### **10.4 Sensitivity Analyses for SVR**

A sensitivity analysis of SVR12 will be conducted using a Modified Intent-to-Treat Genotype and Virologic Failure (mITT-GT -VF) population. The number and percentage of subjects in the mITT-GT-VF population achieving SVR12 and the corresponding 95% Wilson score confidence interval will be calculated.

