The concordance between SVR12 and SVR24 will be assessed by the agreement between SVR12 and SVR24 and by the positive predictive value (PPV) and negative predictive value (NPV) of SVR12 on SVR24. The agreement between SVR12 and SVR24 is a percentage defined as the number of subjects achieving both SVR12 and SVR24 and the number of subjects not achieving both SVR12 and SVR24 out of all subjects in the ITT population. The PPV of SVR12 on SVR24 is the proportion of subjects who achieve SVR12 and SVR24 out of all subjects who achieved SVR12. The NPV of SVR12 on SVR24 is the proportion of subjects who do not achieve SVR12 and SVR24 out of all subjects who did not achieve SVR12.

The number and percentage of subjects who fail to suppress HCV RNA and received at least 6 weeks of treatment (study drug duration  $\geq$  36 days) will be tabulated per treatment arm along with the subject numbers corresponding to the subjects who failed to suppress.

The number of subjects who breakthrough at any time during treatment and within each protocol-specified visit (defined in Table 1 and Table 2) will be summarized along with a corresponding listing displaying the subject numbers at the first occurrence of breakthrough.

The number of completers (defined as DAA duration  $\geq$  161 days and pegIFN/RBV duration  $\geq$  252 days) who relapse within the SVR4 window, within the SVR12 window, within the SVR24 window (defined in Table 3), outside of the SVR24 window (PR end day > 210), and anytime post-treatment, Relapseoverall, (study drug end day  $\geq$  2) will be summarized along with a corresponding listing displaying the first occurrence of relapse. A similar table and listing will be provided of Preterm Relapses for subjects who prematurely discontinued study drug (defined as DAA duration < 161 days and/or pegIFN/RBV duration < 252 days).

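### The mITT-GT-VF set does not define virologic failure; read through the SAP's own reason list it drops relapse after early stopping, and any resulting error in SVR12 is upward

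*SAP*

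**What the plan says.** **The population.** SAP 5.1 takes the ITT set and removes subjects without genotype 1 infection and those who missed SVR12 "for reasons other than virologic failure (mITT-GT-VF"). It does not define virologic failure or refer to any list of reasons. SAP 10.4 uses the set once: a sensitivity analysis of SVR12 "will be conducted using a Modified Intent-to-Treat Genotype and Virologic Failure (mITT-GT -VF) population". It is the only SVR sensitivity analysis, and SAP 12.0 records it as an addition to the protocol.

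**The reasons for SVR12 non-response (SAP 10.1).** There are five.
- Reason 1 is on-treatment virologic failure: breakthrough, or failure to suppress "with at least 6 weeks (defined as active study drug duration" of 36 days or more).
- Reason 2 is relapse, using the Relapse12 "definition for subjects who complete treatment". Completion means DAA duration of at least 161 days and pegIFN/RBV duration of at least 252 days.
- Reason 3 is "Prematurely discontinued study drug with no on-treatment virologic failure".
- Reasons 4 and 5 are missing data and other.

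**The protocol.** Section 5.4.1.1 opens its list with "The following criteria will be considered evidence of virologic failure". The list includes not reaching HCV RNA below 1,000 IU/mL at TI Week 4 and confirmed breakthrough or relapse. Neither has a completion requirement or a minimum treatment duration.

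**Related outputs.** The primary analysis is ITT: "Efficacy analyses will be performed on the ITT population". SAP 10.5 adds: "A similar table and listing will be provided of Preterm Relapses for subjects who prematurely discontinued study drug". SAP 10.6 cites Section 5.4.1.1 for virologic failure, but only for the resistance analyses. The SAP has no section of that number, so the protocol's must be meant.

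**The concern.** The analysis is evidently meant to show SVR12 once non-virologic failures are set aside. It does that only if every subject with virologic evidence of failure stays in the denominator. The SAP offers two candidate definitions, and they give different denominators. A programmer who uses the SAP 10.1 list will remove some subjects whose virus returned. One who uses Protocol 5.4.1.1 will keep them.

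Under the first reading, the same subject can be a virologic failure in the resistance listings, a relapse in the Preterm Relapses table, and absent from the mITT-GT-VF denominator. With up to 35 subjects planned, one or two reclassifications visibly move the rate. The choice would also be made in programming, with the data already known in this open-label trial.

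**Working it through.** The documents give no expected SVR12, power or failure counts, so there is no stated figure to reproduce. The check traces each failure path through SAP 10.1 and then sizes the effect with assumed counts.

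**Step 1: relapse after early stopping.** Take a subject below LLOQ at the Final Treatment Visit who stopped before 161 days of DAA or 252 days of pegIFN/RBV and then has confirmed HCV RNA at or above LLOQ by the SVR12 assessment.
- SAP 10.1: not reason 1 (no on-treatment failure) and not reason 2 (not a completer), so reason 3.
- Protocol 5.4.1.1: confirmed relapse, so virologic failure.
- Result: dropped under the SAP 10.1 reading, kept under the protocol reading.

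The thresholds are lenient for pegIFN/RBV (252/336 = 75% of 48 weeks) and tight for DAA (161/168 = 96% of 24 weeks). A subject who completes DAAs and stops pegIFN/RBV after Week 36 still counts under Relapse12.

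**Step 2: TI Week 4 non-response.** Protocol 5.4.1.1 stops the DAAs and leaves pegIFN/RBV to the investigator. The SAP 10.1 outcome depends on what follows.
- All drugs stopped before 36 days and never below LLOQ: reason 3, dropped. By the SAP 9.0 rule for pegIFN (last minus first injection date plus 7), five weekly injections from Day 1 give 29 − 1 + 7 = 35 days, one short. A sixth gives 36 − 1 + 7 = 42.
- pegIFN/RBV continued to 36 days or beyond and never below LLOQ: kept if *active study drug* includes pegIFN/RBV; dropped if it means DAAs only and DAA duration is under 36 days. The SAP does not say which.
- Suppressed on pegIFN/RBV, then breakthrough: reason 1, kept.
- Suppressed on pegIFN/RBV, then relapse after treatment: dropped. DAAs stopped around Week 4 cannot reach 161 days, even if 48 weeks of pegIFN/RBV are completed.

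**Step 3: direction.** Let S be the SVR12 responders, D the denominator with all virologic failures kept, and m the virologic failures placed in reason 3. The gap is

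S/(D − m) − S/D = S·m / [D(D − m)],

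which is never negative. Misplaced subjects are non-responders, so they leave the denominator and never the numerator.

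**Step 4: size.** Assumed, not from the documents: all 35 planned subjects enrolled and genotype 1, and 2 truly non-virologic failures removed, so D = 33. Intervals are 95% Wilson. With S = 26 and m = 3 (leaving 4 failures that the SAP list counts):

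| Set | Rate | 95% CI |
|---|---|---|
| ITT | 26/35 = 74.3% | 57.9–85.8 |
| mITT-GT-VF, SAP 10.1 reading | 26/30 = 86.7% | 70.3–94.7 |
| mITT-GT-VF, all virologic failures kept | 26/33 = 78.8% | 62.2–89.3 |

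Gap: 26 × 3 / (33 × 30) = 7.9 points.

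Varying m at S = 26: m = 0 gives 0; m = 1 gives 26/(33 × 32) = 2.5 points; m = 5 gives 130/(33 × 28) = 14.1 points.

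Varying S at m = 3: S = 18 gives 5.5 points, S = 22 gives 6.7, S = 30 gives 9.1. Divided by three, that is about 2 to 3 points per misplaced subject.

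**The case against.** A reader might infer that the analysis definitely removes these subjects and therefore overstates SVR12. The documents do not support that. SAP 5.1 does not point to the SAP 10.1 list, and the SAP's one explicit source for unqualified virologic failure is Protocol 5.4.1.1, under which they stay in. This objection stands: the defect is an undefined term whose most natural reading within the SAP is the wrong one, not an explicit instruction to delete. That citation covers only the resistance analyses, so it does not settle the matter either.

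A reader might also infer that every TI Week 4 non-responder is lost. Step 2 shows that this holds only on some paths.

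Nor can it fairly be said that the reason table is mislabelled. Reason 3 claims only that there was no on-treatment failure, which is true of someone who relapses after stopping. It merges subjects with and without viral relapse, which is a loss of information rather than an error.

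The limits also come from the protocol. Section 8.1.3.3 has the same 36-day rule and restricts relapse to subjects completing treatment. That stands as an explanation. But there the limits define failure and relapse rates; the protocol has no mITT-GT-VF set, so they were not written to decide who leaves an SVR12 denominator.

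Finally, the consequence is contained. The ITT analysis counts all these subjects as failures, non-responders are listed, and Preterm Relapses have their own table and listing. All of that stands and limits the severity.

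**Conclusion.** The concern holds in a limited form. SAP 5.1 leaves virologic failure undefined. If the SAP 10.1 reasons govern, confirmed relapse after stopping short of the completion thresholds is dropped from mITT-GT-VF, contrary to Protocol 5.4.1.1. So is relapse in a subject whose DAAs were stopped for TI Week 4 non-response and who then suppressed on pegIFN/RBV. A Week 4 non-responder who never suppresses is dropped only if all drugs stop before 36 days, or if the 36-day rule counts DAAs alone and DAA duration falls short.

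Any error is upward, at about 2 to 3 points per such subject with 35 enrolled and the assumed counts above. It is zero if no such subject occurs or if the protocol definition is applied. It affects one added sensitivity analysis and not the primary result. It is worth correcting before lock because it is cheap and the present wording permits two denominators.

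**What to change.** - In SAP 5.1, define virologic failure for mITT-GT-VF as any Protocol 5.4.1.1 criterion met, or post-treatment relapse regardless of treatment duration. Relapse should be confirmed, or rest on a last available value at or above LLOQ, as SAP 10.1 already allows. Exclude as failures only SVR12 non-responders with no virologic evidence of failure.
- In SAP 10.1, split reason 3 into premature discontinuation with and without viral relapse.
- In SAP 10.1, state whether *active study drug* in the 36-day rule includes pegIFN/RBV.

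The cost is a few sentences and one changed flag, using HCV RNA and dosing data already collected. The downside for the sponsor is a possibly less favourable sensitivity figure. The primary analysis and the clinical stopping rules do not change.

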#### **Safety Population**

Subjects who receive at least one dose of study drug will be included in the safety population. The safety population will be the same as the ITT population for this study.

Safety, demographic, and baseline characteristics will be analyzed for the safety population. No imputations for missing data will be performed for analyses of safety data.

## **5.2 Variables Used for Stratification of Randomization**

There is no randomization for this study.

## **6.0 Analysis Conventions**

The final analyses will be conducted by statisticians and statistical programmers at AbbVie according to the methodologies specified in this SAP. Any deviations from the planned statistical analysis will be described and justified in the final clinical study report, as appropriate.

### **6.1 Definition of Baseline and Final Assessment**

#### **Definition of Baseline**

The baseline value refers to the last non-missing measurement collected before the first dose of study drug is received. All assessments on Study Day 1 should be performed prior to administering the first dose of study drug per protocol. The baseline value is therefore determined by the last non-missing measurement collected on or before the first day of study drug administration.

If multiple measurements are recorded on the same day, the last measurement recorded prior to dosing will be used as Baseline. If these multiple measurements occur at the same time or time is not available, then the average of these measurements (for continuous data) or the worst among these measurements (for categorical data) will be considered as the baseline value. This same baseline value will be used for the TI, PR, and PT Periods.

#### **Definition of Study Days (Days Relative to the First Dose of Study Drug)**

Study days are calculated for each time point relative to the first dose of study drug. They are defined as the number of days between the day of the first dose of study drug and the

specific time point. Study days are negative values when the time point of interest is prior to the first study drug dose day. Study days are positive values when the time point of interest is after the first study drug dose day. The day of the first dose of study drug is defined as Study Day 1, while the day prior to the first study drug dose is defined as Study Day -1 (i.e., there is no Study Day 0).

**Definition of DAA Study Drug End Days (Days Relative to the Last Dose of DAA Study Drug)**

DAA Study Drug End Days are calculated relative to the last dose of DAA study drug. The last day of DAA study drug is defined as DAA Study Drug End Day 0. Days before it have negative DAA Study Drug End Days and days after it have positive DAA Study Drug End Days.

**Definition of Final DAA Treatment Visit Value**

The Final DAA Treatment Visit value is defined as the last non-missing measurement collected after Study Day 1 and on or before DAA Study Drug End Day 2.

**Definition of Study Drug End Days (Days Relative to the Last Dose of pegIFN/RBV)**

Study drug end Days are calculated relative to the last pegIFN injection + 7 days. The last day of pegIFN injection + 7 days is defined as Study drug end Day 0. Days before it have negative Study drug end Days and days after it have positive Study drug end Days.

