5.1.4 Post-Treatment Follow-Up Period (Substudy 3)

In Substudy 3, the Post-treatment (PT) Period, subjects will be followed for 48 weeks after the last dose of study drugs for evaluation of the emergence, evolution and persistence of viral resistance to ABT-450/r and ABT-267 and for viral response.

[figure not shown]
All subjects who receive at least 1 dose of DAA will be monitored for viral resistance on an outpatient basis for an additional 48 weeks following the last dose of study drugs, regardless of whether they prematurely discontinue study drug treatment or complete treatment as planned in Substudies 1 and 2. Refer to [Figure 3](#), Subject Flow Chart.

Subjects will return to the study site as outlined in [Table 7](#) (and [Table 8](#) for cirrhotic subjects) for post-treatment visit procedures including resistance monitoring, HCV RNA testing, and assessment of adverse events (for 30 days post-treatment only) and serious adverse events. Substudy 3 will begin the day after the last dose of study drug treatment. Subjects who prematurely discontinue Substudy 3 should return to the site for a PT Week 48/PT Discontinuation Visit as outlined in [Table 7](#) (and [Table 8](#) for cirrhotic subjects).

Some of the Post-Treatment Period study visits and visit activities (including but not limited to vital signs, clinical laboratory tests and concomitant medication assessment) may be conducted in the home or non-hospital/clinic environment at the request of the Investigator and with the agreement of the subject.

All subjects who receive at least one dose of DAA may be offered participation in a separate AbbVie-sponsored observational study to evaluate the durability of virologic response for subjects who achieve SVR or to study the emergence and persistence of resistant variants in subjects who fail treatment.

Figure 3. Subject Flow Chart

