The subject will write on the pegIFN kit the date (s) and approximate time the injection (s) was/were taken. The subject will return the empty pegIFN kit(s) at each study dispensation visit and discontinuation visit as indicated in [Table 5](#). Study site personnel will inspect the pegIFN kit(s) returned and transcribe the date each injection was taken in the subject's source as well as record the number of syringes used and the date of reconciliation in the IRT system. (For Canadian sites, pegIFN and RBV are co-packaged into one kit so only the RBV drug return will be captured in the IRT and pegIFN accountability will be documented using paper accountability forms.) In all cases, if poor compliance is noted, the subject should be counseled and this should be documented in the subject's source.

Dose modifications, interruptions or discontinuations of pegIFN or RBV should be undertaken in accordance with local prescribing information.

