8.1.3.1 Primary Efficacy Endpoints

The primary efficacy endpoint is the percentage of subjects with sustained virologic response 12 weeks after the last actual dose of study drug (including DAA, pegIFN, and RBV) (SVR_{12actual}; HCV RNA < LLOQ 12 weeks after the last actual dose of study drug). The percentage of subjects with SVR_{12actual} and the corresponding 95% exact binomial confidence interval will be calculated overall and by treatment group in the prior study.

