**Table 3. Post-Treatment (Substudy 3) Visit Windows**

Scheduled Time	Nominal (Study Drug End Day)	Time Window (Study Drug End Days Range)
PT Week 2	14	3 to 21
PT Week 4	28	22 to 42
PT Week 8	56	43 to 70
PT Week 12	84	71 to 126
PT Week 24	168	127 to 210
PT Week 36	252	211 to 294
PT Week 48	336	295 to 378
Final Post-Treatment Visit	Study drug end day > 2	
SVR 4	28	3 to 56
SVR 12	84	57 to 126
SVR 24	168	127 to 210

Notes: The result closest to the scheduled timepoint will be used, except for SVR endpoints. For SVR windows, the last value in the window will be used.

Blood samples for chemistry, hematology, and urinalysis are only scheduled to be collected at PT Weeks 2 and 4 during the Post-Treatment Period.

HCV RNA measurements taken after the start of another anti-viral treatment will be excluded.

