#### **11.2.2 SAEs (Including Deaths) and Adverse Events Leading to Study Drug Discontinuation**

The number and percent of subjects experiencing treatment-emergent SAEs (including deaths), treatment-emergent adverse events leading to discontinuation of study drug (all study drugs), treatment-emergent adverse events leading to interruption of study drug (all study drugs), treatment-emergent adverse events leading to RBV dose modifications, treatment-emergent adverse events leading to pegIFN dose modifications, and treatment-emergent adverse events leading to death will be tabulated according to the primary SOC and PT.

In addition, the number and percentage of subjects with adverse events leading to RBV dose modifications and adverse events leading to pegIFN dose modifications will be tabulated according to the primary SOC and PT, using adverse events with an onset date greater than 30 days post-DAA dosing through 30 days after the last dose of

pegIFN/RBV. For these summaries, only subjects with the maximum of (last RBV dose date, last pegIFN dose date + 7) greater than DAA Study Drug End Day 1 (e.g., last DAA dose date + 1) will be included.

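### Study Drug End Day 0 is set from the last pegIFN injection alone, so when pegIFN stops before the DAAs or RBV the SVR windows and the Final Treatment Visit are placed too early

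*SAP*

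**What the plan says.** Protocol Section 8.1.3.1 reads the primary endpoint "12 weeks after the last actual dose of study drug (including DAA, pegIFN, and RBV"). SAP Section 10.1 uses the same rule for SVR12, "12 weeks after the last actual dose of study drug [including DAA, pegIFN, and RBV"], with the matching rule for SVR24. All three components count.

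The variable that places samples in time is defined differently. In SAP Section 6.1, "Study drug end Days are calculated relative to the last pegIFN injection + 7 days", although the heading of that definition names both pegIFN and RBV. The Final Treatment Visit value (up to Study Drug End Day 2), the Final Post-Treatment value (after End Day 2) and every window in Table 3 rest on it. Table 3 puts SVR12 at End Days 57 to 126, nominal 84, and adds that "For SVR windows, the last value in the window will be used". Its only exclusion is that "HCV RNA measurements taken after the start of another anti-viral treatment will be excluded". Nothing in it requires the DAAs and RBV to have ended.

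Elsewhere the SAP uses a broader rule. For some adverse event tables, Section 11.2.2 includes "only subjects with the maximum of (last RBV dose date, last pegIFN dose date + 7") after the end of DAA dosing.

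The protocol allows the drugs to stop separately. Section 5.5.6 states: "Dose modifications, interruptions or discontinuations of pegIFN or RBV should be undertaken in accordance with local prescribing information". Section 5.4.1 records end dates for each DAA, ritonavir, RBV and pegIFN. Post-treatment visits follow the true end of therapy: "Substudy 3 will begin the day after the last dose of study drug treatment" (Section 5.1.4).

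**The concern.** Visits are scheduled from the last dose of any drug, while analysis windows are counted from the last pegIFN injection. If pegIFN stops first, the two clocks separate. Samples taken on DAA or RBV then fall in windows labelled post-treatment, and the true PT Week 12 sample can leave the SVR12 window. The verbal definition in Section 10.1 does not prevent this, because it is applied through the Table 3 window. The primary endpoint, SVR24, SVR4, Final Treatment Visit Response and the split between breakthrough and relapse all depend on this day. SAP Section 12.1.1, which lists departures from the protocol, does not mention it.

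**Working it through.** **Inputs.** Day 0 = last pegIFN + 7 (SAP 6.1). Windows: SVR4 3–56, SVR12 57–126, SVR24 127–210, last value used (SAP Table 3). PT visits at Weeks 2, 4, 8, 12 and 24 after the last dose (protocol Table 7). Up to 35 subjects (protocol synopsis). Visits on their nominal days are an assumption.

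**Planned regimen.** 48 weekly injections from Day 1: the last is on 1 + 47 × 7 = Day 330, so Day 0 = 337. The last RBV dose is on Day 336 and PT Week 12 on 336 + 84 = Day 420. Its End Day is 420 − 337 = 83, next to the nominal 84. The plan works when the drugs stop together.

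**General rule.** Let g = (last dose of any study drug) − (last pegIFN + 7). PT Week w falls on End Day g + 7w and is inside the SVR12 window only if g + 7w ≤ 126.

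| Gap g (days) | Last scheduled sample in the SVR12 window |
|---|---|
| up to 42 (126 − 84) | PT Week 12, as intended |
| 43–70 (126 − 56) | PT Week 8 |
| 71–98 (126 − 28) | PT Week 4 |
| 99–112 (126 − 14) | PT Week 2 |
| 113 or more | on-treatment or last-dose-day samples only |

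**Example, g = 83.** The 12th and last injection is on Day 78, so Day 0 = 85; DAA and RBV run to Day 168. The SVR12 window covers Study Days 142–211. It holds TI Week 24 (Day 168, End Day 83, on drug), PT Week 2 (Day 182, 97) and PT Week 4 (Day 196, 111). PT Week 8 (Day 224, 139) and PT Week 12 (Day 252, 167) fall in the SVR24 window. SVR12 is therefore read 28 days after the last dose, and a first relapse at PT Week 8 does not count against it. The TI Week 24 sample belongs to a treatment window in Table 1 and to a post-treatment window in Table 3.

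**Example, g = 132.** Last injection Day 29, Day 0 = 36, DAA and RBV to Day 168. The SVR12 window covers Study Days 93–162, and SVR12 is read at TI Week 20 (Day 140), 28 days before the last DAA dose.

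**Short gap, g = 6.** Only the 48th injection is missed: the last is on Day 323, so Day 0 = 330. A PR Final sample on Day 336, still on RBV, is End Day 6, past the End Day 2 cut-off. The Final Treatment Visit falls back to PR Week 12 (168 + 84 = Day 252), because a subject who completed Substudy 1 has no PR Week 24 visit. SVR12 is still read at PT Week 12 (End Day 420 − 330 = 90). But if HCV RNA is below LLOQ on Day 252, quantifiable on Day 336 and again at PT Week 2, the SAP calls it Relapse12. With Day 0 = 336 it would be on-treatment breakthrough.

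**Opposite direction.** Last injection Day 1, Day 0 = 8, other drugs continue. TI Week 2 (End Day 14 − 8 = 6) and TI Week 4 (End Day 28 − 8 = 20) count as post-treatment. If both are at or above 25 IU/mL, the subject has a confirmed quantifiable post-treatment value and fails SVR12, even if later cured.

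**Size.** 1/35 = 2.9 points. For illustration, 28/35 = 80.0% (Wilson 64.1 to 90.0) against 29/35 = 82.9% (67.3 to 91.9).

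**After the fix.** With Day 0 as the latest of the three dates, PT Week 12 falls on End Day 83 or 84 in every stopping pattern examined, and no on-treatment sample enters 57–126.

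**The case against.** The best defence is that the trigger is uncommon. The protocol mostly treats pegIFN and RBV as a pair, many of its stopping rules act on all study drugs, and its explicit single-drug rules concern RBV (pregnancy, renal function, hemoglobin). If RBV stops first, pegIFN + 7 still serves. The study is single-arm and descriptive. In the g = 83 example, a relapse by PT Week 12 would also show as SVR12 achieved and SVR24 not achieved in the concordance analysis. All of this stands as a limit on size. It does not remove the contradiction: stopping pegIFN first is not ruled out, and the concordance table would expose a wrong SVR12 without correcting it.

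Several stronger readings are tempting but not supported:

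- A reader might infer that any early stop of pegIFN spoils SVR12. Up to a 42-day gap, SVR12 is still read at PT Week 12.
- A reader might infer that the error always favours the regimen. The opposite-direction example shows otherwise, and a subject suppressed at both the early and the true reading is scored correctly.
- A reader might infer that RBV continuing into Substudy 2 makes SVR12 wholly on-treatment. With Day 0 = 85 and RBV to Day 182, PT Week 2 is Day 196, inside the window and off drug. RBV must run to Day 198 (gap 113) before no post-treatment visit remains.
- A reader might infer that all secondary and relapse results are affected. The eRVR windows come from Table 1, which uses Study Day and DAA end. Relapse12 and Relapse overall are limited to completers. If the 252-day rule applies to pegIFN itself, Day 0 is at least 253, so with RBV to Day 336 the gap is at most 83 days.

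**Conclusion.** The point holds as a contradiction between the stated primary endpoint and its derivation. When pegIFN stops first, the Table 3 windows and the Final Treatment Visit are early by the length of the gap. SVR12 loses the true PT Week 12 sample above 42 days and rests on no post-treatment visit from 113 days. Shorter gaps can still misplace the Final Treatment Visit and turn a breakthrough into a relapse. The direction of error is not fixed.

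The documents do not give the number of affected subjects, and it may be zero. If k of 35 are misscored in the same direction, SVR12 moves by k/35: 0 points for none, 2.9 for one, 5.7 for two. The thresholds assume visits on nominal days; the stopping dates are illustrative. Subjects who stop the drugs together, or whose pegIFN stops last, are unaffected.

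**What to change.** In SAP Section 6.1, define Study Drug End Day 0 as the latest of the last DAA dose date, the last RBV dose date and the last pegIFN injection date + 7 days. Use it for Table 3, the Final Treatment Visit, the Final Post-Treatment value and the relapse rules. Replace PR end day, used in the Table 2 notes and Section 10.5 but not defined in Section 6.1, with a defined term.

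The cost is one sentence, one derivation line and the terminology edits. Protocol Section 5.4.1 already has the end dates on the eCRF, so no new data are needed. Results do not change for subjects whose pegIFN + 7 is already the latest date.
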